10.1 Immunogenicity Sampling Schedule

A total of 6 immunogenicity blood samples will be collected: pre-start of infusion and at 96, 336, 504, 672, and 1416 hours post-start of infusion.

This document is confidential.

11. Safety

Safety and tolerability analysis will be performed for all subjects in the Safety Population. Safety and tolerability data will be reported using descriptive statistics. No inferential statistical analysis of safety data is planned.

Safety and tolerability to NS101 will be evaluated through the assessment of AEs (i.e., seriousness, severity, relationship to the study drug, outcome, duration, and management), vital signs, 12-lead ECG, clinical laboratory parameters, weight, and physical examination. treatment-emergent adverse events (TEAEs) will be tabulated by study treatment. Changes from baseline values in vital signs, ECG, and clinical laboratory parameters tabulated by study treatment will be evaluated.

11.1 Extent of Exposure

Study drug administration will be listed. The exposure to each dose will be summarized by treatment and overall.

11.2 Adverse Events (AEs)

AEs will be coded using the latest version of the Medical Dictionary for Regulatory Activities (MedDRA). AEs will be grouped by system organ class (SOC) and PT and summarized by actual treatment. The summary tables will present the number and percentage of total subjects and number of events by SOC and by PT.

An AE is defined as any untoward medical occurrence in a clinical study subject after providing written informed consent for participation in the study that does not necessarily have a causal relationship with the study treatment. An AE can therefore be any unfavorable and unintended sign (including an abnormal laboratory finding), symptom, or disease temporally associated with the use of a medicinal (investigational) product, whether or not it is related to the medicinal (investigational) product.

The severity of AEs will be graded according to criteria from the latest version of the Common Terminology Criteria for Adverse Events (CTCAE). The CTCAE displays Grades 1 through 5 with unique clinical descriptions of severity for each AE. Each AE must be classified based on medical judgment and according to the following relationship categories: probable, possible, remote/unlikely, and unrelated.

All AE summaries will include TEAEs only. TEAEs are defined as AEs that commence on or after the time of first study drug administration. AEs without an onset date or time or AEs with an onset date of the date of first study drug administration but without an onset time will be defined as treatment emergent, except if an incomplete date (e.g., month and year) clearly indicates that the event started prior to administration of first study drug or if the AE stop date indicates that the event started and stopped prior to administration of first study drug.

TEAEs will be summarized by treatment. The number and percentage of subjects experiencing AEs and the number of TEAEs will be tabulated. Subjects who experience the same AE (in terms of MedDRA PT) more than once will only be counted once for that event, however, the total number of events will also be counted per category. This also applies to sub-categories displayed in the summaries.

The following summaries will be presented:

This document is confidential.

- Overall summary of TEAEs
- TEAEs by SOC and PT
- TEAEs by SOC, PT, and severity
- TEAEs by SOC, PT, and relationship to study drug
- Serious TEAEs by SOC and PT
- TEAEs with overall occurrence greater than 5% by SOC and PT

All AEs will be listed. This will include a separate listing of serious AEs (SAEs) and Non-TEAEs.

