11.6 Study Treatments Administration

The study treatment will be administered in bed by IV infusion using aseptic techniques. Detailed instructions for study treatment infusion will be included in Pharmacy forms and/or Project Specific Procedure (PSP).

The body weight of each subject measured on Day -1 (check-in) will be used to calculate the exact individual dose required on a mg/kg basis, based on their assigned dose level (cohort), as presented in Table 12. The infusion will be performed over a period of approximately 60 minutes at a constant rate using a volume-controlled infusion device.

Table 12. Dose Levels per Cohort

Cohort	Dose levels of NS101*
1	1 x 0.25 mg/kg
2	1 x 0.75 mg/kg
3	1 x 1.50 mg/kg
4	1 x 3.0 mg/kg
5	1 x 6.0 mg/kg
6	1 x 12.0 mg/kg
7	1 x 24.0 mg/kg
8	1 x 48.0 mg/kg

^{*} Volume of NS101 placebo will be also determined based on subject weight and NS101 concentration.

As an example, for a human weighing 60 kg assigned to the first dose level of 0.25 mg/kg, the administered dose would be equal to 15 mg.

Approximately 1 hour prior to start of study drug infusion, an IV port will be inserted into the antecubital region and a sterile normal saline solution infusion will be initiated at fixed rate in order to keep the vein open. The study drug will be infused over approximately 60 minutes at a constant rate. At the end of the infusion, 3 mL of saline solution will be injected to flush the remaining drug into the IV catheter. The end of infusion will be set to the end of the 3 mL flush. For safety reason (e.g., administration of rescue medication), the IV line will remain opened for approximately 1 hour following completion of infusion.

The start and end times of infusion of each subject will be recorded in the source documents. Time of dosing will be set as the start of study treatment infusion.

Diluted NS101 should be used within 4 hours at room temperature. Diluted NS101 stored at 2°C to 8°C should be equilibrated to room temperature for 30 minutes prior to infusion.

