11.14.2 Recording of Adverse Events

AEs will be recorded and evaluated for their seriousness, severity, and relationship to the study medication. AEs will be collected and documented from signing of ICF and throughout the course of the study. For a period of 60 days following the study treatment administration, AEs will be also documented, if reported. AEs will be followed-up until complete resolution, or until the Investigator judges it to be safe to discontinue follow-up. The relationship to the study treatment will be classified according to the clinical site SOPs.

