3.6 Subject Withdrawal and Replacement

Subjects who withdraw, or are withdrawn, from the study for safety and tolerability reasons after

This document is confidential.

dosing will not be replaced. However, subjects who withdraw or are withdrawn from the study after dosing for reasons other than safety and tolerability, may be replaced. The total number of subjects dosed (including potential replacement subjects) will remain within a maximum of 10 subjects per cohort.

This document is confidential.

4. Endpoints

- Primary endpoints:
 - Incidence, nature, relatedness, and severity of AEs.
 - Changes in vital signs measurements, physical examination, clinical laboratory test findings, and 12-lead electrocardiogram (ECG) results.
- Secondary endpoints:
 - Serum PK parameters for NS101 will include the following:
 - area under the concentration-time curve, from time zero to 24-hours (AUC_{0-24})
 - area under the concentration-time curve from time zero until the last observed concentration (AUC_{0-t})
 - area under the concentration-time curve from time zero to infinity ($AUC_{0-\infty}$)
 - maximum observed concentration (C_{max})
 - time when the maximum concentration is observed (T_{max})
 - terminal elimination half-life ($T_{1/2 el}$)
 - elimination rate constant (K_{el})
 - apparent body clearance (Cl)
 - apparent volume of distribution (V_z)
 - Concentrations of NS101 in CSF for Cohorts 5 to 8
 - Serum to CSF ratio of NS101 concentrations
 - Immunogenicity of NS101, measured as the number and percentage of subjects who develop detectable anti-drug antibody (ADA) and neutralizing antibody (NAb)
- Exploratory endpoints:
 - Effect (E): variation of level of FAM19A5 ($\Delta FAM19A5$) following administration of NS101:
 - PD: Change in baseline of FAM19A5 levels
 - The following PD parameters in plasma:
 - $AUEC_{0-t}$
 - maximal observed effect (E_{max})
 - time of maximal observed effect (TE_{max})
 - Concentrations of FAM19A5 in CSF

This document is confidential.

5. Analysis Populations

All subjects' inclusion status into each analysis population will be determined after database lock.

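### SAP 11.2 has no worsening clause in its TEAE definition, so an AE that begins before the infusion and worsens after it can be absent from every AE summary table

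*SAP*

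**What the plan says.** SAP 11.2 defines treatment emergence by onset alone: "TEAEs are defined as AEs that commence on or after the time of first study drug administration". It also says "All AE summaries will include TEAEs only", and all six AE tables listed there are TEAE tables, including those by severity, by relationship and for serious events. The AE table by ADA status in SAP section 10 is also TEAE-based. The only further rule in SAP 11.2 concerns incomplete dates. It counts "AEs without an onset date or time", and day-of-dosing events without a time, as treatment-emergent unless the available dates show otherwise.

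On collection, Protocol 11.14.2 says "AEs will be collected and documented from signing of ICF and throughout the course of the study". Screening can begin 28 days before dosing (Protocol section 4), so AEs with a pre-infusion onset can exist in the database. Events outside the TEAE definition are listed. SAP 11.2 plans a listing of all AEs and adds "This will include a separate listing of serious AEs (SAEs) and Non-TEAEs".

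Protocol 13.2 tabulates TEAEs but does not define the term and leaves the detail to the SAP. SAP 11.2 is therefore the only operative rule.

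The primary endpoints in SAP section 4 have two parts: "Incidence, nature, relatedness, and severity of AEs", and "Changes in vital signs measurements, physical examination, clinical laboratory test findings, and 12-lead electrocardiogram (ECG) results".

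**The concern.** A TEAE definition usually has two limbs: events that are new after dosing, and events already present that get worse after dosing. The SAP has only the first. Suppose a subject reports a grade 1 headache on Day -1, and it becomes a grade 3 headache judged possibly related after the infusion. If the site keeps one AE record with the Day -1 onset, the event is not treatment-emergent. It then adds nothing to the incidence, severity or relationship tables. If it also becomes serious, it is missing from the serious-TEAE table too.

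The first primary endpoint is about the incidence, severity and relatedness of AEs. For a record of this kind, the rule removes exactly the post-dose change in severity that the endpoint is meant to describe. Dose groups are small, so a single case is visible in a column.

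**Working it through.** The documents state no power, alpha or event rate that depends on this rule, so there is no planned figure to reproduce. The check is a reading of the text plus simple arithmetic on the cohort sizes.

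**Step 1: can such an event occur?** AEs are collected from consent (Protocol 11.14.2) and the infusion comes later, so a pre-infusion AE is possible. Headache is a plausible example. Protocol 11.7.1 stops xanthines from 48 hours before dosing, and Protocol 5.4.1 names headache as a risk of lumbar puncture, which is done in Cohorts 5 to 8. The link to xanthine withdrawal is my assumption; neither document mentions it.

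**Step 2: where does it go if the worsening stays under the original record?**

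| Output | Includes it? |
|---|---|
| Overall TEAE summary; TEAEs by SOC and PT | No |
| TEAEs by severity; by relationship | No |
| Serious TEAEs | No |
| TEAEs above 5% overall | No |
| TEAEs by ADA status (SAP section 10) | No |
| Listing of all AEs; Non-TEAE listing | Yes |
| SAE listing | Yes, if serious |

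**Step 3: is the worsening tabulated elsewhere?**
- Laboratory tests, vital signs and ECG: yes. SAP 11.3 to 11.5 plan change-from-baseline summaries and shift tables that do not depend on TEAE status.
- Injection site: yes. SAP 11.9 tabulates the scores, which Protocol 11.9.7 collects before the infusion and out to 168 hours.
- Physical examination: partly. Under SAP 11.6 a post-dose finding judged a clinically significant change from baseline is recorded as an AE.
- Symptoms such as headache: no other table.

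**Step 4: the weight of one omitted subject.** Each of the 8 cohorts has 6 active and 2 placebo subjects (Protocol 8.1), and placebo is pooled (SAP 6.1).
- Planned totals: 8 × 6 = 48 active, 8 × 2 = 16 placebo, 64 in all. This matches Protocol 10.1.
- One dose column: 1/6 = 16.7 percentage points.
- Pooled placebo: 1/16 = 6.25 points.
- All subjects: 1/64 = 1.6 points.

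These are maxima. The any-TEAE row moves by this amount only if the subject has no other TEAE. Otherwise only the row for that SOC or PT, or its severity or relationship category, changes.

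**Step 5: the table of TEAEs above 5%.** Assume the denominator is all 64 subjects. A term then needs 4 subjects (4/64 = 6.25%), since 3/64 = 4.7% falls short. One omission can remove a term that would otherwise just qualify.

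**Step 6: how often?** The documents give no rate. As illustration only, assume a per-subject probability p of such an event. The chance of at least one among 64 is 1 − (1 − p)^64: 47% for p = 1% and 96% for p = 5%. These values of p are assumptions, not estimates.

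**The case against.** The strongest objection is that the omission depends on data-entry rules not available here. If a grade increase is entered as a new AE line with a post-dose start, it meets the SAP definition and is tabulated. SAP section 1 relies on eCRF completion guidelines, which may require this. The one explicit statement, SAP 11.6 on physical examination, points that way. This stands as a limit on confidence. It does not close the gap, because neither document states the rule for symptoms or for a rise in grade of an ongoing AE.

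Several stronger readings are tempting but unsupported.

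- *The event is lost from all primary-endpoint tables.* It is not. The second part of the primary endpoint has its own change and shift tables. Only the AE summary tables are affected.
- *Injection-site reactions are the main casualty, because* "Approximately 1 hour prior to start of study drug infusion, an IV port will be inserted into the antecubital region". Site scores have their own frequency table, and Protocol 11.9.7 does not list reactions under 10 mm as AEs unless they persist beyond 24 hours.
- *Infusion reactions are missed.* Protocol 11.10 describes them as arising during or after the infusion, so their onset makes them TEAEs. A headache first appearing after lumbar puncture would ordinarily also be a new event with its own onset.
- *The SAP's AE rules bias counts downward only.* The missing clause can only lower counts and maximum grade for the records it affects. The default for undated AEs works in the other direction, so the net direction cannot be stated.
- *Safety decisions are compromised.* The stopping rules in Protocol 9.2 use grade, seriousness and relationship, not TEAE status. All AEs are listed, and no inferential safety analysis is planned.

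**Conclusion.** The point holds in a limited form. SAP 11.2 states an onset-only rule and makes every AE summary depend on it. A pre-infusion AE that rises in grade or becomes serious afterwards, under its original record, is therefore absent from the AE summary tables and visible only in listings. This is a stated rule that gives the wrong count for the first primary endpoint, rather than missing detail. The exposure is mainly symptomatic AEs.

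The frequency is unknown and probably low in healthy volunteers. The size is at most 16.7 points of a dose column or 6.25 points of pooled placebo per omitted subject. The conclusion assumes planned cohort sizes and that worsening is not already entered as a new record; the second assumption could not be checked. The change should be made, but the matter is a correction to the definition and not a threat to the trial's safety oversight.

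**What to change.** In SAP 11.2, define a TEAE as an AE that starts at or after the start of infusion, or that was present before it and afterwards increases in CTCAE grade or becomes serious. The start of infusion is already the time of dosing in Protocol 11.6. Tabulate a worsened event at its post-dose maximum grade and post-dose relationship.

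Confirm whether the eCRF completion guidelines require worsening to be entered as a new AE line with its own start time. If they do, one SAP sentence saying so is enough alongside the definition. If they do not, identify AEs with pre-dose onset that were ongoing at infusion by blinded review before database lock. That avoids reopening the eCRF: version 3.00 is already in place, and results up to Cohort 4 had been reviewed when Cohorts 7 and 8 were added.

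The cost is a short SAP edit, a brief review of what should be few records, and possibly slightly higher TEAE counts. Sample size, allocation and clinical procedures do not change.

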11.3 Clinical Laboratory Evaluations

The following clinical laboratory evaluations will be performed: biochemistry, hematology, coagulation, serology, and urinalysis.

Clinical laboratory values will be flagged as either high or low based on the reference ranges provided by the laboratories for each laboratory parameter.

Actual values and changes from baseline for quantitative clinical laboratory test results will be summarized by cohort/treatment for each time point using descriptive statistics (n, mean, SD, min, median, and max). Unscheduled visits will not be included in the summary tables (unless they were used as baseline).

Shift tables from baseline to each scheduled post-baseline visit, will be generated for categorical clinical laboratory test results using normal; abnormal (NCS, CS), or missing categories as appropriate by cohort/treatment for each time point for the safety set.

Individual clinical laboratory results and reference ranges will be presented in data listings. Unscheduled visits will be included in data listings.

11.4 Vital Signs

Actual values and change from baseline will be summarized by cohort/treatment at each time point using descriptive statistics. Classifications of findings will be shown in a shift table with changes from baseline to post baseline, in addition to being included in the listings. The classifications of findings include “normal”, “abnormal, not clinically significant”, or “abnormal, clinically significant”. Orthostatic vital signs were collected for Cohort 1 to 4. Orthostatic vital signs collection stopped due to Protocol Amendment II and only screening visit data for subject 4001 to 4005 are applicable for cohort 4. These data will be listed separately.

11.5 12-Lead ECG

Actual values and change from baseline for the ECG parameters will be summarized by cohort/treatment at each timepoint using descriptive statistics.

Findings of 12-lead ECGs will be classified as either “normal”, “abnormal, not clinically significant”, or “abnormal, clinically significant”. A shift table for categorical variables will also be created.

All safety ECG data will be listed.

This document is confidential.

11.6 Physical Examination

A complete physical examination includes assessments of the following: head, eyes, ears, nose, throat (HEENT), neck, chest, lungs, abdomen, musculoskeletal, dermatological, cardiovascular/peripheral vascular, and general neurological examination.

A brief physical examination includes assessments of the following: HEENT, chest, lungs, abdomen, dermatological, cardiovascular/peripheral vascular, and areas of note elicited from the subject.

All physical examination data will be listed. Any abnormal finding noted after dosing will be documented as an AE if judged as a clinically significant change from baseline.

11.7 Drug and Alcohol Screens

Results for drug and alcohol screens will be presented in a separate listing for the Safety Population.

11.8 Sheehan Suicidality Tracking Scale (S-STS)

A listing of S-STS Total score will be provided.

11.9 Injection Site Evaluation

Injection site evaluation scores will be tabulated with frequency counts and percentages. A listing of injection site evaluation data will be provided. Bleeding or fluid loss at the injection site will be documented.

11.10 Pulse Oximetry

Pulse Oximetry data will be listed.

11.11 COVID-19 Visit Impact

COVID-19 Visit Impact data will be listed.

This document is confidential.

12. Changes from Analysis Planned in Protocol

None.

This document is confidential.

13. Reference List

This document is confidential.

14. Programming Considerations

- All TLFs, and statistical analyses will be generated using SAS for Windows, Release 9.4.
- Phoenix® WinNonlin® version 8.3.4 (Certara USA, Inc., Princeton, NJ) will be used for all PK analyses. This software was validated by Syneos in compliance with US 21 CFR Part 11 regulation.

14.1 General Considerations

- One SAS program can create several outputs.
- Each output will be stored in a separate file.
- Output files will be delivered in rich text format (RTF) that can be manipulated in MS Word.
- Numbering of TLFs will follow International Conference on Harmonization of Technical Requirements for Registration of Pharmaceuticals for Human Use (ICH) guideline E3 on Structure and Content of Clinical Study Reports, which was approved in 1996. Table, Listing, and Figure Format.

This document is confidential.

14.1.1 General

- All TLFs will be produced in landscape format, unless otherwise specified.
- All TLFs will be produced using the Times New Roman font, size 10. The font size may be reduced as necessary to allow additional columns to be presented, but not at the expense of clarity. The orientation may be changed to portrait, if appropriate.
- The data displays for all TLFs will have a minimum blank 1-inch margin on all 4 sides.
- Headers and footers for figures will be in Times New Roman font, size 10.
- Legends will be used for all figures with more than 1 variable, group, or item displayed.
- TLFs will be in black and white (no color), unless otherwise specified
- Specialized text styles, such as bolding, italics, borders, shading, and superscripted and subscripted text, will not be used in the TLFs, unless otherwise specified. On some occasions, superscripts 1, 2, or 3 may be used (see below).
- Only standard keyboard characters will be used in the TLFs. Special characters, such as non-printable control characters, printer-specific, or font-specific characters, will not be used. Hexadecimal-derived characters will be used, where possible, if they are appropriate to help display math symbols (e.g., μ). Certain subscripts and superscripts (e.g., cm_2 , C_{max}) will be employed on a case-by-case basis.
- Mixed case will be used for all titles, footnotes, column headers, and programmer-supplied formats, as appropriate.

14.1.2 Headers

- All output should have the following header at the top left of each page: “Protocol NS101_P1_01 (200242)”.
- All output should have Page n of N at the top or bottom right corner of each page. TLFs are internally paginated in relation to the total length (i.e., the page number should appear sequentially as page n of N, where N is the total number of pages in the table).
- The SAS system date and time output was generated should appear along with the program name as a footer on each page.

This document is confidential.

14.1.3 Display Titles

Each TFL is identified by the designation and a numeral (e.g., Table 14.1.1). ICH E3 numbering is strongly recommended, but Sponsor preferences are obtained before final determination. A decimal system (x.y and x.y.z) are used to identify TLFs with related contents. The title is left-justified. The analysis set are identified on the line immediately following the title. The title and table designation are single spaced. A solid line spanning the margins will separate the display titles from the column headers. There will be 1 blank line between the last title and the solid line.

For example:

Table x.y.z

First Line of Title

Second Line of Title

